3.1.6 Derivation of RECIST visit responses

For all subjects, the RECIST tumor response data will be used to determine each subject's visit response according to RECIST version 1.1 (see further details in Appendix F in the CSP). It will also be used to

determine if and when a subject has progressed in accordance with RECIST and also their best objective response to study treatment.

Baseline radiological tumor assessments are to be performed no more than 21 days before the first administration of study intervention and ideally as close as possible to the start of study treatment. Tumor assessments are then performed every [CC1] ± 1 week following start of study treatment for the first 36 weeks, then every [CC1] ± 1 week thereafter until objective disease progression.

If an unscheduled assessment is performed, and the subject has not progressed, every attempt should be made to perform the subsequent assessments at their scheduled visits. This schedule is to be followed in order to minimize any unintentional bias caused by some subjects being assessed at a different frequency than other subjects.

From the investigator's review of the imaging scans, the RECIST tumor response data will be used to determine each subject's visit response according to RECIST version 1.1. At each visit, subjects will be programmatically assigned a RECIST v1.1 visit response of complete response (CR), partial response (PR), stable disease (SD) or progressive disease (PD), using the information from target lesions (TLs), non-target lesions (NTLs) and new lesions and depending on the status of their disease compared with baseline and previous assessments. If a subject has had a tumor assessment which cannot be evaluated, then the subject will be assigned a visit response of not evaluable (NE) (unless there is evidence of progression in which case the response will be assigned as PD).

Please see below in Section 3.1.6.1 the definitions of CR, PR, SD and PD.

RECIST outcomes will be calculated programmatically for the site investigator data (see Section 3.2) from the overall visit responses.

3.1.6.1 Target lesions (TLs)

Measurable disease is defined as having at least one measurable lesion, not previously irradiated, which is ≥ 10 mm in the longest diameter (LD) (except lymph nodes which must have short axis ≥ 15 mm) with computed tomography (CT) or magnetic resonance imaging (MRI) and which is suitable for accurate repeated measurements. A subject can have a maximum of 5 measurable lesions recorded at baseline with a maximum of 2 lesions per organ (representative of all lesions involved and suitable for accurate repeated measurement) and these are referred to as TLs. If more than one baseline scan is recorded, then measurements from the one that is closest and prior to first administration of study intervention will be used to define the baseline sum of TLs. It may be the case that, on occasion, the largest lesion does not lend itself to reproducible measurement in which circumstance the next largest lesion, which can be measured reproducibly, should be selected.

All other lesions (or sites of disease) not recorded as TL should be identified as NTLs at baseline. Measurements are not required for these lesions, but their status should be followed at subsequent visits.

Note: For subjects who do not have measurable disease at entry (i.e. no TLs) but have non-measurable disease, evaluation of overall visit responses will be based on the overall NTL assessment and the absence/presence of new lesions (see section Overall visit response for further details). If a subject does not have measurable disease at baseline, then the TL visit response will be not applicable (NA).

Please note, that having non-measurable disease at baseline is violating inclusion criteria 8. In consequence, we don't expect any subjects who do not have measurable disease at entry.

Target lesion tumor size will be windowed to map assessments to analysis visits according to Section 3.1.4 and Appendix C.

Table 4 TL visit responses (RECIST v1.1)

Visit Responses	Description
Complete Response (CR)	Disappearance of all TLs. Any pathological lymph nodes selected as TLs must have a reduction in short axis to <10mm.
Partial response (PR)	At least a 30% decrease in the sum of diameters of TLs, taking as reference the baseline sum of diameters, as long as criteria for PD are not met.
Progressive disease (PD)	A $\geq 20\%$ increase in the sum of diameters of TLs and an absolute increase of $\geq 5\text{mm}$, taking as reference the smallest sum of diameters since treatment started including the baseline sum of diameters.
Stable disease (SD)	Neither sufficient shrinkage to qualify for PR nor sufficient increase to qualify for PD
Not Evaluable (NE)	Only relevant in certain situations (i.e. if any of the target lesions were not assessed or not evaluable or had a lesion intervention at this visit; and scaling up could not be performed for lesions with interventions). Note: If the sum of diameters meets the progressive disease criteria, progressive disease overrides not evaluable as a target lesion response
Not applicable (NA)	No TLs are recorded at baseline (Not expected, because of inclusion criteria 8)

Rounding of TL data

For calculation of PD and PR for TLs percentage changes from baseline and previous minimum should be rounded to 1 decimal place before assigning a TL response. For example, 19.95% should be rounded to 20.0% but 19.94% should be rounded to 19.9%.

Missing TL data

If all TL measurements are missing, then the TL visit response is not evaluable (NE). Overall visit response will also be NE, unless there is a progression of non-TLs or new lesions, in which case the response will be PD.

Lymph nodes

For lymph nodes, if the size reduces to < 10mm then these are considered non-pathological. However, a size will still be given and this size should still be used to determine the TL visit response as normal. In the special case where all lymph nodes are < 10mm and all other TLs are 0mm then although the sum may be >0mm the calculation of TL response should be over-written as a CR.

TL visit responses subsequent to CR

A CR can only be followed by CR, PD or NE. If a CR has occurred, then the following rules at the subsequent visits must be applied:

- Step 1: If all lesions meet the CR criteria (i.e. 0mm or < 10mm for lymph nodes) then response will be set to CR irrespective of whether the criteria for PD of TL is also met i.e. if the sum of diameters for lymph node short axis increases by 20% but all lymph node TL remain < 10mm.
- Step 2: If some lesion measurements are missing but all other lesions meet the CR criteria (i.e. 0mm or < 10mm for lymph nodes) then response will be set to NE irrespective of whether, when referencing the sum of TL diameters, the criteria for PD are also met.
- Step 3: If not all lesions meet the CR criteria and the sum of lesions meets the criteria for PD, then response will be set to PD.
- Step 4: If after steps 1 – 3 a response can still not be determined the response will be set to remain as CR.

TL too big to measure

If a TL becomes too big to measure this should be indicated in the database and a size ('x') above which it cannot be accurately measured should be recorded. If using a value of x in the calculation of TL response would not give an overall visit response of PD, then this will be flagged and reviewed by the study team, if appropriate blinded to treatment assignment. It is expected that a visit response of PD will remain in the vast majority of cases.

TL too small to measure

If a TL becomes too small to measure, then this will be indicated as such on the case report form and a value of 5mm will be entered into the database and used in TL calculations. However, a smaller value may be used if the radiologist has not indicated 'too small to measure' on the case report form and has entered a smaller value that can be reliably measured. If a TL response results in PD, then this will be reviewed by the study team.

Irradiated lesions/lesion intervention

Previously irradiated lesions (i.e. lesion irradiated prior to entry into the study) should be recorded as NTLs and should not form part of the TL assessment.

Any TL (including lymph nodes), which has had intervention during the study (for example, irradiation/ palliative surgery/ embolisation), should be handled in the following way and once a lesion has had

intervention then it should be treated as having intervention for the remainder of the study noting that an intervention will most likely shrink the size of tumors:

- Step 1: the diameters of the TLs (including the lesions that have had intervention) will be summed and the calculation will be performed in the usual manner. If the visit response is PD this will remain as a valid response category.
- Step 2: If there was no evidence of progression after step 1, treat the lesion diameter (for those lesions with intervention) as missing and if $\leq 1/3$ of the TLs have missing measurements then scale up as described in the ‘Scaling’ section below. If the scaling results in a visit response of PD then the subject would be assigned a TL response of PD.
- Step 3: If, after both steps, PD has not been assigned, then, if appropriate (i.e. if $\leq 1/3$ of the TLs have missing measurements), the scaled sum of diameters calculated in step 2 should be used, and PR or SD then assigned as the visit response. Subjects with intervention are evaluable for CR as long as all non-intervened lesions are 0 (or <10 mm for lymph nodes) and the lesions that have been subject to intervention have a value of 0 (or <10 mm for lymph nodes) recorded. If scaling up is not appropriate due to too few non-missing measurements, then the visit response will be set as NE.

At subsequent visits the above steps will be repeated to determine the TL and overall visit response. When calculating the previous minimum, lesions with intervention should be treated as missing and scaled up (as per step 2 above).

Scaling

If $> 1/3$ of TL measurements are missing, then TL response will be NE, unless the sum of diameters of non-missing TL would result in PD (i.e. if using a value of 0 for missing lesions, the sum of diameters has still increased by 20% or more compared to nadir and the sum of TLs has increased by ≥ 5 mm from nadir).

If $\leq 1/3$ of the TL measurements are missing, then the results will be scaled up (based on the sizes at the nadir visit) to give an estimated sum of diameters and this will be used in calculations; this is equivalent to comparing the visit sum of diameters of the non-missing lesions to the nadir sum of diameters excluding the lesions with missing measurements.

Example of scaling

Lesion 5 is missing at the follow-up visit; it had a BL measure of 29.3 cm. The sum of lesions 1-4 at the follow-up is 26 cm. The sum of the corresponding lesions at nadir visit is 26.8 cm.

Scale up as follows to give an estimated TL sum of 28.4 cm:

$$\frac{26}{26.8} \times 29.3 = 28.4 \text{ cm}$$

CR will not be allowed as a TL response for visits where there is missing data. Only PR, SD or PD (or NE) could be assigned as the TL visit response in these cases. However, for visits with $\leq 1/3$ lesion assessments not recorded, the scaled up sum of TLs diameters will be included when defining the nadir value for the assessment of progression.

Lesions that split in two

If a TL splits in two, then the LDs of the split lesions should be summed and reported as the LD for the lesion that split.

Lesions that merge

If two TLs merge, then the LD of the merged lesion should be recorded for one of the TL sizes and the other TL size should be recorded as 0 cm.

Change in method of assessment of TLs

CT, MRI and clinical examination are the only methods of assessment that can be used within a trial, with CT and MRI being the preferred methods and clinical examination only used in special cases. If a change in method of assessment occurs between CT and MRI this will be considered acceptable and no adjustment within the programming is needed.

If a change in method involves clinical examination (e.g. CT changes to clinical examination or vice versa), any affected lesions should be treated as missing. The TL visit response may still be evaluable if the number of missing TL measurements at a visit is $\leq 1/3$ of the total number of TLs.

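### After a target-lesion CR, a visit with one lesion unmeasured, a measured lesion no longer meeting CR and a sum short of PD defaults to CR, against the SAP's ban on CR with missing data

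*SAP*

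**What the plan says.** SAP section 3.1.6.1 sets a special rule for visits after a target-lesion (TL) CR: "A CR can only be followed by CR, PD or NE". Four steps must then be worked through in order.

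- **Step 1** gives CR if every lesion still meets CR (0 mm, or below 10 mm for a node).
- **Step 2** covers missing data: "If some lesion measurements are missing but all other lesions meet the CR criteria", "then response will be set to NE irrespective of whether, when referencing the sum of TL diameters", PD is met as well.
- **Step 3** gives PD: "If not all lesions meet the CR criteria and the sum of lesions meets the criteria for PD".
- **Step 4** is the default if, after the first three, "a response can still not be determined the response will be set to remain as CR".

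The Scaling paragraphs of the same section deal with unmeasured lesions at any visit. They state: "CR will not be allowed as a TL response for visits where there is missing data". They add: "Only PR, SD or PD (or NE) could be assigned as the TL visit response in these cases". When more than one third "of TL measurements are missing, then TL response will be NE, unless the sum of diameters of non-missing TL would result in PD".

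SAP section 3.1.6 says visit responses are assigned by program. Neither document says which of the two sets of rules takes precedence.

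**The concern.** Step 2 is the only one of the four steps that mentions missing measurements, and it applies only while every measured lesion still meets CR. Once a measured lesion fails CR, the visit leaves Step 2. If the sum is short of PD, it also misses Step 3 and falls to Step 4, which has no exception for missing lesions. The program then returns the one response that the Scaling text forbids, and the order of outcomes is reversed: a scan with regrowth is rated above a scan without it.

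Three listed items could change. The first is the visit response: under SAP Table 6, a TL CR with non-target lesions (NTLs) in CR or not applicable, and no new lesion, is an overall CR. The second is the PFS censoring date, because a CR visit is evaluable and an NE visit is not. The third, in a narrower case, is the best objective response (BOR).

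**Working it through.** **Inputs from the documents.** CR for a node: below 10 mm (SAP Table 4). PD: an increase of at least 20% and at least 5 mm over the smallest sum (SAP Table 4). With up to one third of lesions missing, the sum is scaled up from the nadir visit (SAP 3.1.6.1, Scaling).

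**Inputs assumed.** Three TLs. At the CR visit, which is taken as the nadir, node A is 9 mm, node B is 8 mm and lesion C is 0 mm, so the sum is 17 mm. At the next visit B is not measured (one third of the TLs) and C is 0 mm. Only A varies.

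**Formula.** Scaled sum = (measured lesions now ÷ the same lesions at nadir) × full nadir sum. The SAP's own example reproduces: 26 ÷ 26.8 × 29.3 = 28.43, stated as 28.4.

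| Node A | Scaled sum | Change from 17 mm | Step reached | Response |
|---|---|---|---|---|
| 9 mm | not used | not used | 2 | NE |
| 10 mm | 10/9 × 17 = 18.89 | +1.89 mm, +11.1% | 4 | CR |
| 11 mm | 11/9 × 17 = 20.78 | +3.78 mm, +22.2% | 4 | CR |
| 12 mm | 12/9 × 17 = 22.67 | +5.67 mm, +33.3% | 3 | PD |

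As node A grows, the sequence is NE, CR, PD.

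**Other way of handling the missing lesion.** The SAP also describes scaling as comparing the measured lesions with their own nadir. The percentages are the same, but the 5 mm condition is then harder to meet: 13 against 9 mm is +4 mm (CR by Step 4), and 14 against 9 mm is +5 mm (PD). The CR band widens to 10–13 mm.

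**More than one third missing.** Take two nodal TLs, 9 and 8 mm, with the second unmeasured and counted as 0. The literal steps give NE at 9 mm and CR at 10, 12, 15 and 20 mm (20 against 17 is +3 mm, +17.6%). They give PD at 22 mm (+5 mm, +29.4%). The Scaling text says NE for all the non-PD sizes.

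**Which response satisfies both rules.** After a CR, the allowed set is CR, PD or NE. With missing TL data it is PR, SD, PD or NE. The overlap is PD or NE, so a visit short of PD can only be NE.

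**Effect on PFS.** SAP section 3.2.2.1 censors at the last evaluable assessment. If the affected scan is the last one, rating it CR instead of NE moves the censoring date by one scan interval: about 6 weeks, or 8 after Week 36.

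**Effect on BOR.** BOR uses overall visit responses (SAP section 3.2.3.2). If the earlier TL CR came with NTLs not yet in CR, Table 6 made that visit an overall PR. If the NTLs are in CR at the affected visit, Step 4 makes it an overall CR, and BOR moves from PR to CR.

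**The case against.** The strongest reply is that the text already settles the matter: the Scaling ban has no exceptions and, with the post-CR rule, leaves NE as the only non-PD answer. That deduction is sound and it supports the fix. It does not remove the conflict, because Step 4 looks back only to Steps 1 to 3 and no precedence is stated. A programmer following the numbered steps gets CR.

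Three limits stand.

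- **The sum must be short of PD.** Otherwise Step 3 gives PD.
- **The practical route is a node.** Protocol Appendix F 4.2.1 records a lesion that vanished and reappears as a new lesion, which is overall PD. Nodes below 10 mm keep a recorded size and can regrow without that rule applying.
- **Efficacy is listed only.** Protocol section 9.4.2 and SAP section 4.2.2 drop the efficacy summaries, and 9 patients received the combination.

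A reader might infer that calling a regrown node CR is itself the error. The documents do not support that. With all three lesions measured, A at 10 to 13 mm also gives CR by Step 4 (13 + 8 = 21 mm, +4 mm), because PR and SD are barred after a CR. That is a general convention and is not challenged here. Nor is residual disease on the scan an objection to a censoring date, since PR and SD scans are valid censoring points too.

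**Conclusion.** The point holds in a narrow form. It requires a previous TL CR, at least one TL unmeasured, a measured TL (in practice a node of 10 mm or more) no longer in CR, and a sum short of PD. For that combination Step 4 contradicts the Scaling rule and reverses the order set by Step 2. In the assumed example the affected sizes are 10 and 11 mm on the scaled sum, or 10 to 13 mm on the measured lesions alone. The sizes are illustrative; the thresholds are the SAP's.

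The consequence is small: one subject's listed visit response, one listed PFS censoring date, and BOR only where the earlier visit was an overall PR. A reader might infer a biased PFS estimate. The documents do not support that, because no PFS estimate is planned in the abbreviated report, and nothing shows that the later censoring date would be biased. This is a minor correction, worth making because responses are derived by program.

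**What to change.** Reword Step 4 along these lines: *If Steps 1 to 3 give no response, CR is kept only when no target-lesion measurement is missing at that visit; if any target lesion was not measured, the response is NE.* Add that lesions with an intervention and a recorded measurement continue to follow the lesion-intervention rules. Those rules treat such a lesion as missing for scaling although it has a size, so the new sentence would otherwise be ambiguous for it.

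In the worked example the 10 and 11 mm cases change from CR to NE, the sequence becomes NE, NE, NE, PD, and the reversal disappears. CR for regrowth short of PD with every lesion measured is unchanged.

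The cost is one reworded sentence, one clarifying sentence and one condition in the program. Some post-CR visits with up to one third of lesions missing become NE, although scaling would make them evaluable in a subject without a CR. The two existing rules already require that when read together.

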3.1.6.2 Non-target lesions (NTLs) and new lesions

At each visit, the investigator should record an overall assessment of the NTL response. This section provides the definitions of the criteria used to determine and record overall response for NTL at the investigational site at each visit.

NTL response will be derived based on the Investigator's overall assessment of NTLs as follows:

Table 5 NTL visit responses

Visit responses	Description
Complete Response (CR)	Disappearance of all NTLs present at baseline with all lymph nodes non-pathological in size (<10 mm short axis).
Progressive Disease (PD)	Unequivocal progression of existing NTLs. Unequivocal progression may be due to an important progression in one lesion only or in several lesions. In all cases the progression MUST be clinically significant for the physician to consider changing (or stopping) therapy.
Non-CR/Non-PD	Persistence of one or more NTLs with no evidence of progression.
Not Evaluable (NE)	Only relevant when one or some of the NTLs were not assessed and, in the investigator's opinion, they are not able to provide an evaluable overall NTL assessment at this visit. Note: For subjects without TLs at baseline, this is relevant if any of the NTLs were not assessed at this visit and the progression criteria have not been met.
Not Applicable (NA)	Only relevant if there are no NTLs at baseline

To achieve 'unequivocal progression' on the basis of NTLs, there must be an overall level of substantial worsening in non-target disease such that, even in the presence of SD or PR in TLs, the overall tumor burden has increased sufficiently to merit a determination of disease progression. A modest 'increase' in the size of one or more NTLs is usually not sufficient to qualify for unequivocal progression status.

Details of any new lesions will also be recorded with the date of assessment. The presence of one or more new lesions is assessed as progression.

A lesion identified at a follow-up assessment in an anatomical location that was not scanned at baseline is considered a new lesion and will indicate disease progression.

The finding of a new lesion should be unequivocal: i.e. not attributable to differences in scanning technique, change in imaging modality or findings thought to represent something other than tumor.

New lesions will be identified via a Yes/No tick box. The absence and presence of new lesions at each visit should be listed alongside the TL and NTL visit responses.

A new lesion indicates progression so the overall visit response will be PD irrespective of the TL and NTL response.

If the question ‘Any new lesions since baseline’ has not been answered with Yes or No and the new lesion details are blank this is not evidence that no new lesions are present, but should not overtly affect the derivation.

Symptomatic progression is not a descriptor for progression of NTLs: it is a reason for stopping study therapy and will not be included in any assessment of NTLs.

Subjects with ‘symptomatic progression’ requiring discontinuation of treatment without objective evidence of disease progression at that time should continue to undergo tumor assessments where possible until objective disease progression is observed.

3.1.6.3 Overall visit response

Table 6 defines how the previously defined TL and NTL visit responses will be combined with new lesion information to give an overall visit response.

Table 6 Overall visit responses

TARGET	NON-TARGET	NEW LESIONS	OVERALL VISIT RESPONSE
CR	CR or NA	No (or NE)	CR
CR	Non-CR/Non-PD or NE	No (or NE)	PR
PR	Non-PD or NE or NA	No (or NE)	PR
SD	Non-PD or NE or NA	No (or NE)	SD
PD	Any	Any	PD
Any	PD	Any	PD
Any	Any	Yes	PD
NE	Non-PD or NE or NA	No (or NE)	NE
NA	CR	No (or NE)	CR
NA	Non-CR/Non-PD	No (or NE)	SD
NA	NE	No (or NE)	NE

